6.5.1 Screening Visit

Following written informed consent from each subject, the Investigator will determine whether subjects are eligible to participate in the study by performing screening evaluations.

(-14 Day to Day 0) Screening visit:

- 1. Informed consent.
- 2. Record demographics.
- 3. Review of Inclusion/Exclusion Criteria.
- 4. Women of childbearing potential will be tested for pregnancy with a urine pregnancy test.
- 5. Medical history.
- 6. Concomitant medication.
- 7. Record adverse event, if any.
- 8. Clinical assessment of signs and symptoms of AD Calculate ADSI score of both potential treatment sites.
- 9. Schedule baseline visit

Screening and Day 1 / Baseline visit can be on the same day.

Continuous monitoring of concomitant medications, therapies, and AEs throughout the study period will begin at the Screening visit.

6.5.2 All Other Visits

Study visit assessments and sample collections will be conducted as presented in Tables 2 and 3.

The Screening and Day 1/Baseline visit can be combined for subjects meeting *all* eligibility requirements and only if *all* Screening and Day 1/Baseline tests and tasks can be completed on the same day.

Day 1/Baseline visit:

- 1. Confirm compliance with treatment site restrictions.
- 2. Record any changes in concomitant medications.
- 3. Record adverse event, if any.
- 4. Blinded evaluating investigator complete clinical assessment of severity of signs and symptoms of AD prior to application of test article.
- 5. Calculate ADSI score of both potential treatment sites if the Screening visit was on an earlier date. At Baseline, if ADSI eligibility criterion is no longer met, the subject is to be withdrawn from the study prior to sample collection and test article application.
- 6. Digital images of both treatment sites.
- 7. Collect PBS swabs from both treatment sites.
- 8. Collect samples from both treatment sites.
- 9. Unblinded treating investigator, or designee, to train subjects and/or LAR on method for selfor LAR to apply with a training vial.
- 10. Unblinded treating investigator, or designee, apply test articles after all evaluations and sampling have been completed.
- 11. Blinded evaluating investigator complete clinical assessment of local tolerability (severity pain, burning, or stinging in addition to pruritus, erythema, exudation, excoriation, and lichenification) 30-minutes after application of test articles to both treatment sites.
- 12. Review treatment site restrictions.
- 13. Review procedures for telemed visits.
- 14. Dispense 1% hydrocortisone ointment as needed.
- 15. Schedule appointment for Day 7 clinic visit and telemed visits.

Detailed instructions for sample collection, storage, and shipping are in the Collection Sampling, Storage, Shipping Procedure (CSSSP) provided separately. If violations of treatment site restrictions prior to the visit are reported details of the violation should be recorded in the CRF and the visit should be completed including evaluations and sampling.

DermBiont

Day 7 (±2)

- 1. Confirm compliance with treatment site restrictions.
- 2. Record any changes in concomitant medications.
- 3. Record adverse event, if any.
- 4. Blinded evaluating investigator complete clinical assessment of severity of signs and symptoms of AD.
- 5. Blinded evaluating investigator complete clinical assessment of local tolerability (severity pain, burning, or stinging in addition to pruritus, erythema, exudation, excoriation, and lichenification).
- 6. Calculate ADSI score of both potential treatment sites.
- 7. Digital images of both treatment sites.
- 8. Collect PBS swabs from both treatment sites.
- 9. Unblinded treating investigator, or designee, apply test articles after all evaluations and sampling have been completed.
- 10. Collect used and unused returned test articles.
- 11. Dispense test articles for home treatment.
- 12. Review treatment site restrictions.
- 13. Dispense 1% hydrocortisone ointment as needed.
- 14. Schedule appointment for Day 14 clinic visit and telemed visits.

Detailed instructions for sample collection, storage, and shipping are in CSSSP provided separately. If violations of treatment site restrictions prior to the visit is reported details of the violation should be recorded in the CRF and the visit should be completed including evaluations and sampling.

Day 14 (±2)

- 1. Women of childbearing potential will be tested for pregnancy with a urine pregnancy test.
- 2. Confirm compliance with treatment site restrictions.
- 3. Record any changes in concomitant medications.
- 4. Record adverse event, if any.
- 5. Blinded evaluating investigator complete clinical assessment of severity of signs and symptoms of AD.
- 6. Blinded evaluating investigator complete clinical assessment of local tolerability (severity pain, burning, or stinging in addition to pruritus, erythema, exudation, excoriation, and lichenification).
- 7. Calculate ADSI score of both potential treatment sites.
- 8. Digital images of both treatment sites.

DermBiont

- 9. Collect PBS swabs from both treatment sites.
- 10. Unblinded treating investigator, or designee, apply test articles after all evaluations and sampling have been completed.
- 11. Collect used and unused returned test articles.
- 12. Dispense test articles for home treatment.
- 13. Review treatment site restrictions.
- 14. Dispense 1% hydrocortisone ointment as needed.
- 15. Schedule appointment for Day 21 clinic visit and telemede visits.

Detailed instructions for sample collection, storage, and shipping are in the CSSSP provided separately. If violations of treatment site restrictions prior to the visit is reported details of the violation should be recorded in the CRF and the visit should be completed including evaluations and sampling

Day 21 (±2)

- 1. Confirm compliance with treatment site restrictions.
- 2. Record any changes in concomitant medications.
- 3. Record adverse event, if any.
- 4. Blinded evaluating investigator complete clinical assessment of severity of signs and symptoms of AD.
- 5. Blinded evaluating investigator complete clinical assessment of local tolerability (severity pain, burning, or stinging in addition to pruritus, erythema, exudation, excoriation, and lichenification).
- 6. Calculate ADSI score of both potential treatment sites.
- 7. Digital images of both treatment sites.
- 8. Collect PBS swabs from both treatment sites.
- 9. Unblinded treating investigator, or designee, apply test articles after all evaluations and sampling have been completed.
- 10. Collect used and unused returned test articles.
- 11. Dispense test articles for home treatment.
- 12. Review treatment site restrictions.
- 13. Dispense 1% hydrocortisone ointment as needed.
- 14. Schedule appointment for Day 21 clinic visit and telemed visits.

Detailed instructions for sample collection, storage, and shipping are in the CSSSP provided separately. If violations of treatment site restrictions prior to the visit is reported details of the violation should be recorded in the CRF and the visit should be completed including evaluations and sampling.

Day 28 (±2) Follow up visit (no treatment)

- 1. Confirm compliance with treatment site restrictions
- 2. Record any changes in concomitant medications.
- 3. Record adverse event, if any.
- 4. Blinded evaluating investigator complete clinical assessment of severity of signs and symptoms of AD.
- 5. Blinded evaluating investigator complete clinical assessment of local tolerability (severity pain, burning, or stinging in addition to pruritus, erythema, exudation, excoriation, and lichenification).
- 6. Calculate ADSI score of both potential treatment sites.
- 7. Digital images of both treatment sites
- 8. Collect PBS swabs from both treatment sites
- 9. Collect samples from both treatment sites
- 10. Review treatment site restrictions with subject
- 11. Dispense 1% hydrocortisone ointment as needed
- 12. Schedule appointment for Day 35 clinic visit

Detailed instructions for sample collection, storage, and shipping are in the CSSSP provided separately.

If reported violations of treatment site restrictions occurred more than 24 hours prior to the Day 28 visit, details of the violation should be recorded in the CRF and the evaluations and sampling completed as scheduled.

If reported violations of treatment site restrictions occurred less than 24 hours prior to the Day 28 visit, details of the violation should be recorded in the CRF the evaluations can be completed, but an additional visit 24-48 hours after the violation should be scheduled for sample collections.

Day 35 (±4) Follow up visits (no treatment)

- 1. Confirm compliance with treatment site restrictions.
- 2. Record any changes in concomitant medications.
- 3. Record adverse event, if any.
- 4. Blinded evaluating investigator complete clinical assessment of severity of signs and symptoms of AD.
- 5. Blinded evaluating investigator complete clinical assessment of local tolerability (severity pain, burning, or stinging in addition to pruritus, erythema, exudation, excoriation, and lichenification).
- 6. Calculate ADSI score of both potential treatment sites.
- 7. Digital images of both treatment sites.
- 8. Collect PBS swabs from both treatment sites.
- 9. Review treatment site restrictions.

- 10. Dispense 1% hydrocortisone ointment as needed.
- 11. Schedule appointment for Day 42.

Detailed instructions for sample collection, storage, and shipping are in the CSSSP provided separately.

If reported violations of treatment site restrictions occurred more than 24 hours prior to the Day 35 visit, details of the violation should be recorded in the CRF and the evaluations and sampling completed as scheduled.

If reported violations of treatment site restrictions occurred less than 24 hours prior to the Day 35 visit, details of the violation should be recorded in the CRF the evaluations can be completed, but an additional visit 24-48 hours after the violation should be scheduled for sample collections.

Day 42 (±4) Follow up visits (no treatment)

- 1. Women of childbearing potential will be tested for pregnancy with a urine pregnancy test.
- 2. Confirm compliance with treatment site restrictions
- 3. Record any changes in concomitant medications.
- 4. Record adverse event, if any.
- 5. Blinded evaluating investigator complete clinical assessment of severity of signs and symptoms of AD.
- 6. Blinded evaluating investigator complete clinical assessment of local tolerability (severity pain, burning, or stinging in additional to in addition to pruritus, erythema, exudation, excoriation, and lichenification).
- 7. Calculate ADSI score of both potential treatment sites.
- 8. Digital images of both treatment sites
- 9. Collect PBS swabs from both treatment sites
- 10. Dispense 1% hydrocortisone ointment as needed

Detailed instructions for sample collection, storage, and shipping are in the CSSSP provided separately.

If reported violations of treatment site restrictions reported occurred more than 24 hours prior to the Day 42 visit, details of the violation should be recorded in the CRF and the evaluations and sampling completed as scheduled.

If reported violations of treatment site restrictions occurred less than 24 hours prior to the Day 42 visit, details of the violation should be recorded in the CRF the evaluations can be completed, but an additional visit 24-48 hours after the violation should be scheduled for sample collections.

Study Specific Procedures

Clinical Evaluations:

All primary endpoint assessments must be done by an observing evaluating investigator who is a board-certified dermatologist. Investigators who are not board-certified dermatologists may perform the role of an observing, evaluating investigator at the Sponsor's discretion.

6.6.1 Grading of signs and symptoms of AD using ADSI

Both targeted treatment areas will be evaluated using the ADSI. The ADSI score represents the sum of the individual severity scores on none, mild, moderate, or severe for the following component signs and symptoms: erythema, pruritus, exudation, excoriation and lichenification. The investigators will only be required to calculate the ADSI at the Screening and Baseline visits to confirm that the subjects meet the inclusion criteria for disease severity. The ADSI for subsequent visits will be calculated during data analysis. The same observer-blinded investigator should perform the ADSI grading for each subject for the duration of a subject's participation in the study.

The same signs and symptoms of AD are also commonly use to evaluate application site reactions to topical product and serves a secondary role in characterizing tolerability. The sponsor will consider improvement in the ADSI and the individual signs and symptoms of AD an indicator of either a favorable therapeutic effect or the demonstration of the natural variation of AD over time. If the signs and symptoms increase in severity, the sponsor will consider this an indication of an application site reaction and/or the natural variation in AD over time. To further characterize local tolerability, subject self-reporting of pain, burning, or stinging will also be recorded. Each component is measured using the following scale:

Erythema score: (redness presents specifically in the target lesion)

0=none	No redness
1=mild	Mildly detectable erythema; pink
2=moderate	Dull red; clearly distinguishable
3=severe	Deep, dark red; marked and extensive

Exudation score: (oozing or crusting of the target lesion)

0=none	No oozing or crusting
1=mild	Minor or faint signs of oozing
2=moderate	Definite oozing or crusting present
3=severe	Marked and extensive oozing or crusting present

Excoriation score: (evidence of scratching in the target lesion)

0=none	No evidence of excoriation
1=mild	Slight excoriation present

2=moderate	Definite excoriation present
3=severe	Marked, deep, or extensive excoriation present

Pruritus: as reported by the subject as being the greatest intensity they have experienced within the last 24 hours at Baseline or since the last visit at subsequent visits.

0	None	No pruritus
1	Mild	Slight pruritus, not really bothersome
2	Moderate	Definite pruritus that is somewhat bothersome
3	Severe	Intense pruritus that may interrupt daily activities and/or sleep

Lichenification score: (epidermal thickening of the target lesion)

0=none	No epidermal thickening
1=mild	Minor epidermal thickening
2=moderate	Definite epidermal thickening; accentuated skin lines
3=severe	Marked epidermal thickening; deeply accentuated skin lines

To calculate the ADSI score, the component scores are added together.

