1.2 Rationale

In-vitro has been shown to significantly inhibit the growth of *S. aureus* (DR005 2019) most frequently associated with AD. Application of to the skin of amphibians has been shown to be able to treat and prevent the acquisition of a lethal cutaneous fungal infection. (Harris et al. 2009). In a previous small pilot clinical trial, a single application of DBI001 was well tolerated and resulted in the reduction in the abundance of *S. aureus* and improvement in the signs and symptoms of AD, most noticeable pruritis (DBI-CSR-203). In a clinical trial of subjects with T. pedis 28 daily applications of DBI001 to the entire foot was well tolerated, decreased the abundance of T. rubrum, and improved the signs and symptoms of T. pedis. (DBI-CSR-201, DBI-CSR-204) Based on these observations, topical application of the probiotic has the potential to be a novel approach to the treatment of AD.

POTENTIAL RISKS AND BENEFITS

Potential Risks

Despite the fact that is found in the cutaneous microbiome of some people as well as in the human food chain, it is possible that application of could result in a worsening of the AD, impetigo, folliculitis, or cellulitis. It is possible that could be an opportunistic pathogen in severely immune compromised subjects. PBS solution will be used to collect samples and it could cause a local irritant reaction

As detailed in the Investigator's Brochure, if worsening of the AD, impetigo, or folliculitis or cellulitis were to occur, is susceptible to commonly used topical and oral antimicrobials and antibiotics.

Potential Benefits

It is possible that daily applications of could result in improvement in the subject's AD. Such a treatment also has the potential to decrease the use of oral and topical antibiotics.

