4.2.2 Secondary Endpoints

In the *S. aureus* MITT population, comparison of sites treated with DBI-001 or Aqueous Gel on the following microbial metrics:

- Change from baseline in abundance of *S. aureus* based on molecular diagnostic qPCR and CFU counts on samples obtained from treatment sites at days 7, 14, 21, 28, 35, and 42.
- Abundance of based on qPCR and CFU counts.
- Changes in the abundance and diversity of the microbiome as determined by 16s and/or whole genome sequencing.
- The proportion of subjects with a greater decrease in ADSI for the DBI-001-treated site than the Aqueous Gel-treated site.
- Change from baseline in signs and symptoms of local tolerability (pruritus, erythema, exudation, excoriation, and lichenification as well as pain, burning, or stinging) for the DBI-001-treated lesion and the Aqueous Gel-treated lesion.

INVESTIGATIONAL PRODUCT (IP)

Investigational Product and Aqueous Gel (Test Articles)

Test articles	Doses per Subject
1mL vial contains DBI-001 Gel with 10 ⁷ -10 ⁹ CFU / mL of	27 doses (once daily for 4 weeks)

ELIGIBILTY CRITERIA

Inclusion Criteria

Subjects must meet all of the following criteria to be included in the study:

1. Ability to understand, agree to, and sign the study Informed Consent. If the subject is unable to provide consent for him/herself, the subject's legally authorized representative may provide written consent.

2. A signed Health Information Portability and Accountability Act (HIPAA) authorization form which permits the use and disclosure of subject's individually identifiable health information.

3. Male or Female Subjects of any race 12-65 years of age.

4. Physician diagnosed clinically stable AD according to the criteria of Hanifin and Rajka with comparable anatomically symmetrical, bilateral target lesions (Hanifin and Rajka 1980). Each lesion must have an Atopic Dermatitis Severity Index (ADSI) score of ≥ 6 . It will be in the

opinion of the Investigator based on subject's medical history whether the lesions are clinically stable.

5. Female subjects of child-bearing potential must use at least one method of birth control that results in a low failure rate (i.e., less than 3 % per year) when used consistently and correctly such as implants, injectables, combined oral contraceptives, some intrauterine devices (IUDs), sexual abstinence or vasectomized partner for the duration of study participation.

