6.6.2 Local Tolerability

Tolerability will be evaluated based on calculating the scores for pruritus, erythema, exudation, excoriation, lichenification and the additional symptoms of pain, burning, or stinging using the following scale:

Pain, Burning, or Stinging: as reported by the subject as being the greatest intensity they have experienced within the last 24 hours at Baseline or since the last visit at subsequent visits.

0	None	No pain, burning, or stinging
1	Mild	Slight pain, burning or stinging sensation; not really bothersome
2	Moderate	Definite pain, burning or stinging that is somewhat
		bothersome
3	Severe	Significant pain, burning, or stinging sensation that causes definite
		discomfort and may interrupt daily activities and/or sleep.

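### The pruritus and pain/burning/stinging items do not ask for a separate rating at each target site, so one overall answer would contribute nothing to the left-right comparison

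*Combined protocol and SAP*

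**What the plan says.** Section 6.6.1 builds the ADSI from five items scored 0 to 3 and added together. The four physical signs are located on the lesion, for example "Erythema score: (redness presents specifically in the target lesion" and "Lichenification score: (epidermal thickening of the target lesion"; exudation and excoriation are likewise defined by reference to the target lesion.

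The two subject-reported items are not located. Itch is "Pruritus: as reported by the subject as being the greatest intensity they have experienced within the last 24 hours" at Baseline, with recall running from the previous visit thereafter. Section 6.6.2 uses the same form: "Pain, Burning, or Stinging: as reported by the subject as being the greatest intensity they have experienced within the last 24 hours at Baseline". The top category of both scales refers to interruption of daily activities or sleep, which describes the person and not a site.

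Other parts of the protocol treat these measures as per site:
- 6.6.1 opens by applying the ADSI to both target areas, and the visit lists in 6.5.1 and 6.5.2 ask for a score at both sites.
- 4.2.1 lists change in ADSI and in its components as between-site comparisons. 7.2.1 tests the ADSI by signed-rank test and 7.2.3 tests each component by sign test.
- 4.2.2 compares tolerability, including both subject-reported items, by treated lesion.
- 8.1 places pain, burning or stinging on the treated areas. It does not name pruritus.
- Inclusion criterion 4 is by lesion: "Each lesion must have an Atopic Dermatitis Severity Index (ADSI) score of ≥ 6".

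Disease elsewhere is foreseen. Inclusion criterion 9a and the concomitant medication section supply 1% hydrocortisone for non-target areas, and Table 1 dispenses it as needed from Baseline to Day 42. Section 1.2 reports that a single application in the sponsor's pilot was followed by "improvement in the signs and symptoms of AD, most noticeable pruritis".

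**The concern.** In a within-subject bilateral design, an item carries information about treatment only if it can differ between the two sites. A physical sign on a lesion does so naturally. A symptom does so only if the subject is asked about each site. A subject with itch elsewhere on the body, answering the item as worded, could reasonably give one figure for the worst itch anywhere, and that figure could be entered for both sites.

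At stake is one of the five components of the primary score, and the one the sponsor's rationale singles out. For pain, burning or stinging, the stake is whether a local reaction can be attributed to one side. Neither loss can be recovered at analysis, because the separate answers would never have been collected.

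**Working it through.** **Plan's own figure.** The only relevant figure is the sample size of approximately 20, which 7.5 bases on clinical judgement. No effect size, SD, power or dropout rate is given, so it cannot be reproduced, and any statement about power needs outside assumptions.

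**Wording side by side.**

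| Item | Source | Tied to target lesion? | In ADSI? |
|---|---|---|---|
| Erythema, exudation, excoriation, lichenification | 6.6.1 | Yes, each one | Yes |
| Pruritus | 6.6.1 | No | Yes |
| Pain/burning/stinging | 6.6.2 | Not in the scale; 8.1 says treated areas | No |

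**Cancellation.** Let A and B be the four-sign totals at a visit on the DBI-001 and Aqueous Gel sites, A0 and B0 their baselines, and p and p0 a single itch rating entered for both sites. The contrast in ADSI change is

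(A + p − A0 − p0) − (B + p − B0 − p0) = (A − A0) − (B − B0).

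The itch terms vanish; 1,000 simulated records agreed exactly. The usable maximum per site falls from 5 × 3 = 15 to 4 × 3 = 12. For the pruritus component alone the contrast is (p − p0) − (p − p0) = 0, so the sign test gains nothing from that subject. The same algebra applies to pain/burning/stinging within the tolerability comparison. Exact cancellation needs a shared answer at both baseline and follow-up; if it is shared at only one, the item contributes only the side difference at the other visit.

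**Size, under assumed inputs.** With true benefit b on each sign and c on pruritus, the share of the expected ADSI difference lost when every subject gives a shared answer is c / (4b + c). The power figures assume 20 subjects, normal item differences with SD 0.8 and pairwise correlation 0.3, rounded to whole points, and a two-sided signed-rank test at 0.05 (3,000 runs). None of the effect sizes, SDs or correlations is in the documents.

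| b per sign / c pruritus | Share of difference lost | Power, per site | Power, all shared | Change (points) |
|---|---|---|---|---|
| 0.3 / 0.3 | 0.3/1.5 = 20% | 63.2% | 60.8% | −2.4 |
| 0.3 / 0.6 | 0.6/1.8 = 33% | 79.1% | 59.3% | −19.8 |
| 0.2 / 0.6 | 0.6/1.4 = 43% | 56.3% | 30.7% | −25.6 |
| 0.3 / 0 | 0/1.2 = 0% | 44.6% | 59.4% | +14.8 |

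The equal-benefit loss is small because dropping an item also removes its variance. If about half the subjects give shared answers, power in the 0.2 / 0.6 case is 45.5%, a loss of 56.3 − 45.5 = 10.8 points.

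The figures move with the assumptions. A second run of the 0.2 / 0.6 case gave 58.2 − 29.0 = 29.2 points, so simulation error is a few points. With the correlation at 0 the loss is 86.3 − 51.2 = 35.1 points; at 0.6 it is 40.1 − 23.1 = 17.0. With benefits of 0.1 and 0.8 it is 46.2 − 11.4 = 34.8.

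**The case against.** The strongest reply is that per-site scoring is plainly meant. The ADSI is applied to both areas, the visit lists score both sites, a sign test of pruritus by treatment would be empty under a shared score, and the tolerability endpoint is by lesion. No section says one rating is taken. The CRF, which is not among the documents, may already have right and left fields. This stands as far as intent goes, and it makes the point a risk. It does not dispose of it: these instructions address the investigator and the analyst, while the item the subject answers names no site.

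For pain/burning/stinging, 8.1 goes further. That narrows the gap, but both sites are treated areas, so it still does not separate right from left. The item is outside the ADSI, so the primary comparison is untouched.

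A reader might infer more, and the documents do not support it:
- *Pruritus will drop out of the primary comparison.* This needs shared answers, which no section prescribes.
- *Shared itch admits lesions that are too mild.* Itch of 3 plus three mild signs totals 6 whether or not the itch is site-specific, so that profile follows from the threshold. The synopsis also asks for moderate to severe lesions.
- *The pilot shows a larger side-to-side benefit on itch.* Section 1.2 reports improvement after a single application; it gives no between-site figure and no ratio to the other items.
- *A definite power loss can be quoted.* The result depends on item correlation, relative benefit and the proportion giving shared answers, all unknown.

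**Conclusion.** The concern holds as a wording ambiguity with a definite consequence for each subject it affects. Both subject-reported items lack the lesion wording of the four signs, and neither asks for separate ratings. A subject who gives one overall rating at baseline and follow-up contributes zero for that item. For pruritus, the ADSI contrast then rests on 4 of 5 items and 12 of 15 points, and the component comparison is zero by construction. For pain/burning/stinging, only the tolerability comparison suffers.

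How many subjects would answer this way is unknown, as is the layout of the CRF. If all did, the loss runs from about 2 to about 25 points over the main assumed scenarios and is larger under more extreme inputs; power rises if pruritus has no true benefit. These figures show only that the loss could be negligible or substantial. The case for acting is that the information cannot be recovered later and the correction is small.

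**What to change.** Reword both definitions, in 6.6.1 for itch and 6.6.2 for pain, burning or stinging, along these lines: *the greatest itch [pain, burning or stinging] at this target site, rated separately for right and left*. Leave the recall periods as they are for this purpose. Confirm that the CRF has separate right and left fields for both items at every visit where they are scored, and use the site-specific itch score in the ADSI ≥ 6 check at Screening and Baseline.

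The cost is two sentences and a CRF check, with no added visit or procedure. A small downside is that a few subjects may no longer reach ADSI 6 once itch elsewhere is excluded from the score.
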